Our primary aims are to evaluate the feasibility of a larger study and examine preliminary data regarding benefit and tolerability of an essential oil formulation distributed by Young Living Essential Oils, Lehi, UT., for enhancing QOL in children with ASDs. We will develop preliminary data suitable to be submitted in a competitive NIH grant application for a larger multisite study. The proposed study will include a 7-month crossover with two 3-month conditions and a month washout between, with randomly assigned order. The 2 conditions will be a proprietary formula of essential oils and a scented coconut oil comparator. Measures of QOL, equanimity, and sleep health will include parent report on valid and reliable rating scales.

Primary Hypotheses

1. We can recruit 28 participants in 2 years with 85% adherence and 85% retention through both conditions.

- 2. With essential oils, participants will show significantly improved QOL on the Pediatric Quality of Life Inventory compared to the control condition, with a medium effect size.
- 3. While receiving essential oils participants will show negligible or no increases in adverse events (AEs), including allergic contact dermatitis, immediate contact reactions (contact urticaria), and photosensitivity, compared to the control condition.

Secondary Mediational Hypotheses

- 1. With essential oils, compared to the control condition, participants will show significantly improved sleep onset and maintenance on objective and subjective measures (actigraphy; parent sleep diaries, and parent and clinician-rated scales) with a medium effect size, and this will mediate the improvement in QOL.
- 2. With essential oils, compared to the control condition, participants will display greater equanimity and improvements in mood and daytime behavior on objective and subjective measures (heart rate; parent and clinician rated scale) compared to the control condition and this will mediate the improvement in QOL.

Participant Inclusion/Exclusion Criteria

Inclusion Criteria

Entry criteria are the following:

- i. Outpatients between 3 and 9 years of age, inclusive;
- ii. Diagnosis of Autism Spectrum Disorder (ASD) by DSM-V;
- iii. Total item mean score of > 1.5 on PedsQL Inventory;
- vi. Care provider who can reliably bring subject to clinic visits and provide trustworthy ratings.

Exclusion Criteria

Exclusion criteria are the following:

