To be applied only by a trusted adult or under adult supervision.

Topical: Apply 1 drop to the back of the neck and 1 drop to the feet. Rub in the oil for 30 seconds to 1 minute. Each bottle has an orifice that allows the oil to be expelled drop by drop. Dilution is not required, except for the most sensitive skin. Apply in the morning.

Aromatic Method: Diffuse one diffuser-full (8-12 drops of oil in water) at night.

- 1. Home diffuser instructions: Open the water reservoir by lifting the lid. Add room-temperature water (distilled water is recommended) up to the fill line of the reservoir. Do not exceed the fill line.
- 2. Add 8-12 drops of Reconnect to the water.
- 3. Replace the lid to cover the water reservoir.
- 4. Plug in the Home Diffuser and push the power switch to start diffusing.
- 5. When water runs out, the diffuser will automatically shut off.
- 6. To cycle through the three-mode power settings, press the power switch quickly: Mode 1: Green light Constant diffusion Mode 2: Red light 30 seconds intermittent diffusion Mode 3: Off. Use constant diffusion (green light, mode 1).
- 7. To turn on/off the ambient LED light, press and hold the power switch for approximately 2 seconds.

Notice: Due to the mist output of the Home Diffuser, use caution on surfaces that are sensitive to water.

Essential Oil

The type of Young Living essential oil we will be utilizing is ReconnectTM. ReconnectTM contains the following ingredients: Caprylic/capric triglycerides, Prunus amygdalus dulcis (Sweet almond) oil, Boswellia sacra† oil, Citrus aurantium bergamia† peel oil, Commiphora myrrha oil, Lavandula angustifolia† oil, Pelargonium graveolens† flower oil, Callitris intratropica wood oil, Santalum paniculatum† wood oil, Cananga odorata† flower oil, Cedrus atlantica† wood oil, Aniba rosaeodora† wood oil, Melissa officinalis† leaf oil, Picea pungeons†

branch/leaf/wood oil, Picea mariana leaf oil, Hyssopus officinalis† leaf oil, Rosa damascena† flower oil. The comparison oil is coconut oil with a tiny amount of vanilla, just enough for an aroma. Please see Table 2 for a listing of the ingredients, their current common uses, and potential side effects.

Primary Outcome Measure

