Laboratory Tests. On three separate occasions during the study participants will have blood drawn and laboratory tests will be conducted to assess any changes in test values since the Screening Visit. Blood and urine will be collected at the Screen Visit, at the Endpoint of the first phase (Week 12), and at the Endpoint of the last phase (Week 28). The following tests will be run on the blood samples: ALT, AST, total and direct bilirubin, creatinine, CRP, IL-6, and CBC. The following tests will be run on the urine samples: standard urinalysis, to evaluate protein, PH, glucose, ketones, nitrites, appearance, color, specific gravity, and bacteria.

Adverse Events (AEs). To minimize the risk, subjects will be systematically monitored. AEs, vital signs, including resting BP, will be evaluated at each visit throughout all phases of the study. When the treating clinician elicits an AE, it will be documented on a case report form, regardless of suspected relationship to the essential oil. For all AEs, the investigator will obtain sufficient information to determine the onset, course, and outcome of the AE. If a subject has experienced an AE, the subject may return to the site for an unscheduled visit at the PI's discretion. If any of these AEs are serious and/or unexpected, the site PI will contact the Sponsor and notify the IRB as appropriate.

Potential AEs include sun sensitivity due to the Bergamot in the essential oil, possibly gynecomastia in pre-pubescent males due to the lavender oil in the essential oil, and skin irritation at the application site.

Sample Characteristics

Demographic Profile. This will be completed by the parent / caregiver at screening to document basic demographic information (parent education, occupation, and marital status).

Cognitive / Developmental Measures. Depending on the age and functioning level of the child, the Stanford-Binet Intelligence Scales; 5th Edition abbreviated battery (Nagle & Bell, 1993) or Mullen Scales of Early Learning AGS Edition will be administered (Mullen, 1995). These are the two cognitive/developmental measures used in the Autism Treatment Network and our other projects. We will evaluate level of cognitive functioning to characterize our sample. The IQ test results will be used to characterize our sample via mean and standard deviation.

Social Validity

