Aniba rosaeodora wood oil	Anti-depressant, mildly analgesic, antiseptic, aphrodisiac; helps with headaches	Non-toxic, non-irritating, non-sensitizing; generally regarded as safe	α-pinene, camphene, geraniol, neral, geranial, myrcene, limonene, 1,8-cineole, linalool, benzaldehyde, linalool oxides and a-	Rosewood essential oil information (2014). Esoteric Oil CC . Web.

			terpineol	
Picea mariana (Spruce) leaf oil	Helps with arthritis, infections, and pain; supports the immune system	FDA approved Food Additive and Flavoring Agent; non-toxic and generally safe but could result in skin irritation	Pinenes, limonene, boryl acetate, tricyclene, phellandrene, thujone	Martin, N. (n.d.). Spruce Essential Oil offers Support for Muscles and the Immune System! Experience- Essential-Oils.com. Web.
Hyssopus officinalis leaf oil	Used in cooking; medicinally used as a cough suppressant and expectorant; helps with nervous exhaustion and grief	Contains thujone which stimulates the CNS and can cause seizures as the oil, even in low doses, in children; otherwise non-irritating and non-sensitizing	α-pinene, camphene, β-pinene, sabinene, myrcene, limonene, pinocamphone, isopinocamphene, γ- terpineol, 1,8-cineole and thujone	Woolf, A. (1999). Essential Oil Poisoning. Clinical Toxicology , 37(6), 721-727.
Rosa damascena flower oil	Helps with dry skin/eczema, asthma, heart arrhythmia, high BP; anti- depressant, sedative, laxative, aphrodisiac, anxiolytic	Non-toxic, non-irritating, and non-sensitizing	300+ compounds, but main ones are citronellol, phenyl ethanol, geraniol, nerol, farnesol, stearpoten, α-pinene, myrcene, limonene, menthone, and linalool (Rose)	Woolf, A. (1999). Essential Oil Poisoning. Clinical Toxicology, 37(6), 721-727. Rose geranium essential oil information (2014). Esoteric Oils CC. Web.
Santalum paniculatum (Royal Hawaiian Sandalwood) wood oil	Perfume, meditation, relaxation; Helps chapped skin, scars, and stretch marks; anti-inflammatory, a disinfectant, diuretic, and anti-depressant; said to help with insomnia, bug bites, headaches, depression	May cause skin irritation and should be diluted.	100% steam-distilled pure Sandalwood oil from Hawaiian trees (organic compounds not specified)	"Royal Hawaiian Sandalwood Essential Oil Santalum Paniculatum." Hana Naia Aromatherapy . Hana Naia LLC, 2014. Web.

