				colophony and propolis as screening tools in the detection of fragrance allergy. British Journal of Dermatology, 145: 268–273. doi: 10.1046/j.1365-2133.2001.04345.x Hausen BM. Contact allergy to balsam of Peru. II. Patch test results in 102 patients with selected balsam of Peru constituents. Am J Contact Dermat. 2001;12(2):93–102. [PubMed]
Coconut Oil	Used as a flavoring in foods. Added to some pharmaceuticals and cosmetics. Commonly rubbed on the skin.	Populations of people that consume large quantities of coconut oil show no adverse effects. According to the FDA, "There is no evidence in the available information on coconut oil, peanut oil, and oleic acid that demonstrates, or suggests reasonable grounds to suspect, a hazard to the public as they are now used in paper and cotton packaging material for food at levels now current or as they might reasonably be expected to be used for such purposes in the future."	Composed of 92% saturated fatty oils.	Thampan, P.K., Glimpses of coconut industry in India, Coconut Development Board, Cochin 1988. Krishna, G., Rah, G., Bhatnagar, A. S., Kumar, P., & Chandrashekar, P. Indian Coconut Journal. "Coconut Oil: Chemistry, Production and Its Applications - A Review." 2010. "Select Committee on GRAS Substances (SCOGS) Opinion: Coconut Oil (packaging)." U.S. Food and Drug Administration, Apr. 2013. Web. 02 Jan. 2015.

Human Subjects considerations

Participants:

Participants are 28 children age 3-9 with autism spectrum disorder and excessive anxiety and sleep disturbance. Although we are not treating autism, this population is especially prone to impaired QOL due to sleep problems and anxiety, and is the population for which OTC essential oils are most often used by consumers without adequate test of benefits and safety. Careful evaluation of this practice has been requested by parents of children with autism.

Risks:

Essential oils themselves are generally regarded as safe and are routinely used by the public. One of the purposes of this pilot study is to check whether this assumption is valid. The main known risk/discomfort is from the blood draws, with possible bleeding, bruising, or infection. The ratings pose some time/effort burden for parents and the usual confidentiality risks apply. Although uncommon, skin irritation with topical administration or breast enlargement in boys is a potential side effect of a few ingredients of Reconnect (See Table 2).

Minimization of risk:

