Numbing cream will be offered for blood draws, which will be done by experienced phlebotomists. The usual security for personal health information will be used, with locked files accessible only to CITI-trained and HIPAA-trained research staff and password-protected electronic data. Time/effort burden will be partially compensated by payment. All families will be given phone numbers of the PIs and coordinator to reach in the event of some unexpected adverse event. Potential skin sensitivity and potential male breast enlargement will be checked for at each visit by a physician, who may discontinue the oils or switch mode of administration based on clinical judgment.

Ethnic & Sex Composition of sample:

The sample is expected to reflect the ethnic proportions of central Ohio. Sex ratio is expected to mirror that of the autism population, 4:1 boys. Both males and females will be included in the study.

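### The ingredient table warns that hyssop oil can cause seizures in children, but no adverse-event list, risk text or named visit check mentions seizure

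*Combined protocol and SAP*

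**What the plan says.** The Essential Oil section lists hyssop leaf oil among the ingredients of Reconnect and sends the reader to the ingredient table for safety: "Please see Table 2 for a listing of the ingredients, their current common uses, and potential side effects". The hyssop row says that the oil contains thujone, a CNS stimulant, and "can cause seizures as the oil, even in low doses, in children".

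Four other places name adverse events, risks or checks:

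- **Primary hypothesis 3** expects "negligible or no increases in adverse events (AEs), including allergic contact dermatitis, immediate contact reactions (contact urticaria), and photosensitivity".
- **Safety Measures, Adverse Events**: "Potential AEs include sun sensitivity due to the Bergamot in the essential oil". The list goes on to gynecomastia attributed to lavender and to irritation where the oil is applied.
- **Human Subjects considerations, Risks**: "The main known risk/discomfort is from the blood draws, with possible bleeding, bruising, or infection". For the product itself, the text says that "skin irritation with topical administration or breast enlargement in boys is a potential side effect of a few ingredients of Reconnect", followed by a pointer to Table 2.
- **Minimization of risk**: "Potential skin sensitivity and potential male breast enlargement will be checked for at each visit by a physician".

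Outside Table 2, seizure appears once, in exclusion criterion iii, which removes children with a seizure disorder or epilepsy.

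**The concern.** The plan's own safety table attaches a serious neurological hazard to an ingredient, and attaches it to children in general. The places that tell staff what to expect and look for carry forward milder effects from that table and leave this one out. Rarity does not explain the choice, since the Risks text describes the skin and breast effects it names as uncommon.

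The Risks text says of the assumed safety of essential oils that "One of the purposes of this pilot study is to check whether this assumption is valid", and tolerability is among the primary aims. A brief or night-time episode may not be recognised as a possible seizure, or mentioned, if the question put to the family is a general one. The larger daily quantity is diffused at night (8 to 12 drops in water, against 2 drops on the skin in the morning), and the listed fields of the sleep diary cover sleep timing and awakenings only.

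**Working it through.** No formula applies and the plan gives no figure to reproduce. The check is a comparison of text.

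**Step 1: is the warned ingredient in the product?** The Essential Oil section lists 17 ingredients and Table 2 has 17 rows. Hyssop is in both. Its row is the only one of the 17 with a seizure warning. Thujone also appears in the composition column for *Picea mariana* oil, another ingredient, but without a seizure warning there.

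**Step 2: which Table 2 warnings reach the other places?**

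| Table 2 warning | Hypothesis 3 | Potential-AE list | Risks text | Each-visit checks |
|---|---|---|---|---|
| Skin reaction | yes | yes | yes | yes |
| Sun sensitivity | yes | yes | no | no |
| Breast enlargement | no | yes | yes | yes |
| Headache, nausea (*Cananga odorata*) | no | no | no | no |
| Seizure (hyssop) | no | no | no | no |

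Seizure is named in 0 of 4 places. Skin, sun and breast effects are named in 4, 2 and 3 of them. The headache and nausea row shows that the lists are abridged generally, so seizure was not the only omission.

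**Step 3: what would still catch a seizure?**

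- Criterion iii excludes children with a known seizure disorder. It cannot exclude a child whose first seizure occurs on study.
- Adverse events are evaluated at each visit. Table 1 marks them at V3 to V10, which is 8 visits. The clinician elicits them, and they are recorded regardless of suspected relationship.
- The physician discusses side effects and may stop the oils. Families hold study phone numbers, and unscheduled visits are allowed.
- Serious or unexpected events go to the sponsor and, as appropriate, to the IRB.
- The Risks text points to Table 2, so a reader who follows the pointer finds the hyssop row. The sentence carrying the pointer names only skin irritation and breast enlargement.

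**Step 4: what is left?** Targeted checks exist for skin and breast. For seizure, the available text provides general questioning only, and no instruction on what to do if one is suspected.

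**Step 5: who is exposed?** In a crossover every randomized child is scheduled for Reconnect: 28 children, up to 33 allowing for early dropout, for 12 weeks each.

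**The case against.** The strongest reply is that the plan already covers this. The group most plainly at risk is excluded, a clinician asks about adverse events at every visit from V3, everything elicited is recorded, and the physician can stop treatment. The lists in hypothesis 3 and Safety Measures are worded as open-ended. The sentence on blood draws can be read as describing the main expected burden, without denying other hazards. Reconnect is a 17-ingredient blend that includes carrier oils, used in drops, so the warning about hyssop oil itself may not carry over to it. The case report forms were still to be created, so the AE form may turn out to have a neurological prompt.

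Most of this stands, and it limits the point. A reader might infer that a seizure would be detected only if a parent volunteered it, or that it would go unrecorded. The documents do not support that: the clinician elicits adverse events, and a reported seizure would be captured. A reader might also infer that families are not warned. The consent pages are not available, so nothing can be said about that.

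Two things survive. The exclusion does not answer a warning addressed to children in general. And since Table 2 says that even low doses matter, the plan should not rely on a small dose without stating why that dose is safe.

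One further objection affects the remedy. Because reporting is triggered by an event being serious or unexpected, listing seizure as a potential event could make a brief, non-serious one count as expected and weaken that trigger. The wording has to prevent this.

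**Conclusion.** The point holds as a narrow gap. The seizure warning in Table 2 is absent from all 4 places that name adverse events, risks or checks, and the Risks text reaches it only through a cross-reference attached to other effects. A first seizure is therefore sought by general questioning alone, with no seizure-specific instruction in the available text.

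It would be wrong to conclude that Reconnect is known to carry a seizure risk at the study dose. Table 2 gives no route or concentration for hyssop, and no thujone content is stated, so the risk is unknown and is not estimated here. The conclusion rests on two assumptions: that the AE form, which is not in the documents, has no seizure prompt, and that the consent material has no stop-and-call instruction. If either already exists, the matching part of the fix falls away and the wording changes remain. This is a cheap improvement to child safety and does not touch the efficacy analysis.

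**What to change.** 1. Name seizure in the potential-AE list and in the Risks text. Reword the sentence that ranks blood draws first so that it agrees with Table 2, for example: Table 2 notes that one ingredient, hyssop oil, can cause seizures in children; the risk at the study dose is not known. State that any seizure is still reported promptly to the sponsor and the IRB even though it is now listed.
2. Unless the AE form already has one, add a direct question on suspected seizure at each adverse-event visit (V3 to V10), worded identically in both conditions.
3. Unless the consent material already does so, tell parents to stop the oil and call the study physician at once if they suspect a seizure.

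**Cost.** One form line, one parent instruction and a few sentences, with no new visit or procedure. With full attendance by 28 children, the question is asked 28 × 8 = 224 times. Condition 1 has 4 of these visits (V3 to V6), the end of washout has 1 (V7) and condition 2 has 3 (V8 to V10). With 14 children per order, each oil gets 14 × 4 + 14 × 3 = 98 askings, plus 28 at the end of washout. These counts describe the effort of the fix, not the size of the hazard. A few extra non-specific reports are likely, expected equally in both conditions, so the comparison of adverse events should not be tilted.

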- i. Bipolar disorder by Child & Adolescent Symptom Inventory (CASI, Gadow & Sprafkin, 1997) and clinical interview/history, or major depression accompanied by family history of bipolar disorder;
- ii. Children with allergies to essential oils;
- iii. Children with seizure disorder/epilepsy;
- iv. Significant physical illness (e.g., serious cardiovascular, liver, or renal pathology);
- v. Medications specifically given for insomnia and exogenous melatonin, which have the potential to confound study results, within the previous 2 weeks before baseline;
- vi. Anticipated changes of doses of medication or other medical treatments or supplements;
- vii. Weight less than 10 kg;
- viii. Sleep Disordered Breathing (SDB) as defined by a total score of ≥ 3 on the CSHQ SDB subscale and parent report;
- ix. Nut allergies;
- x. Allergy to vanilla;
- xi. A substantial trial of essential oil use within the past 6 months (i.e., consistent use for 6 weeks).

METHODS

Study Design

This study will use a double-blind -controlled crossover design with random assignment to order of conditions. The 2 conditions will be ReconnectTM, a mixture of essential oils formulated by Young Living (YL) vs. a fragrant appearance-matched coconut-oil comparator. In order to randomize 28 children we anticipate that approximately 36 children will be screened. There will 2 conditions in the crossover design.

Participants will receive Reconnect or scented coconut oil comparator for 3 months following the Baseline visit. At the end of 3 months, participants will be administered all endpoint measures for that condition. Then there will be a 1-month washout prior to the start of the second condition. At the end of the second 3-month condition, participants will again be administered all endpoint measures for that condition. The endpoint assessment for the 2nd condition will be 7 months from original baseline. During the 1st condition participants will be evaluated at 2 week intervals for the first month to assess whether the mode of essential oils application is tolerable (i.e., inhalation or topical application) and to develop graphs of effect on sleep and equanimity over time. During the final 8 weeks of condition one, participants will be seen monthly. During the second condition we will have established that the modes of application are tolerable and subjects will be evaluated at 3 monthly visits. There will be 10 visits to the Center including the Screening and Baseline Visits.

Procedures

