All participants must have significant problems with QOL as measured by the PedsQL Inventory, with a total item mean score of ≥ 1.5 (i.e., one standard deviation below the normative mean).

At baseline, participants will be randomly assigned to one of two orders of essential oils. The oil will be dispensed at the Baseline visit, and will be administered by both massaging the oil on the feet and the back of the neck in the morning and by the diffusion method in the evening.

In this study, clinical responders will be defined as showing a 30% improvement in the total score of the PedsQL Inventory.

Approximately 50% of children will wear a device known as an actigraph that measures activity level and sleep quality. There will be 6 actigraphs and they will be assigned to participants as they are made available on a first come first serve basis. There may be some participants who are unwilling to wear the actigraph and for those who are tactiley defensive we will not require them to do so. Participants will wear the devices for five consecutive nights, on three separate occasions (i.e., between Screening and Baseline, prior to the End Point of the first 3 month period, and prior to the End Point of the second 3 month period). The small watch-like devices worn on the wrist or ankle will collect activity data and measure body temperature while the participant sleeps. They will yield the following sleep variables: 1) time in bed, 2) total sleep time (from lights out), 3) sleep onset latency, 4) morning waking time, 5) frequency of night

wakings, 6) longest sleep period, and 7) sleep efficiency. This is a reliable method of objective data collection for sleep-wake patterns including timing, continuity, and duration of sleep.

In the proposed study, there will be a primary clinician (the physician) and an independent evaluator. The physician will discuss possible side effects and make dose or administration mode adjustments. The independent evaluator will interview the parents with respect to target improvements (QOL) and make DD-CGAS ratings based on all feedback, including parent rating scales.

Dosing

Each participant will utilize both oil delivery methods: diffusion at night and topical application in the morning. If a participant is unable to tolerate one of these delivery methods, then both the morning and night-time doses can be administered via the same, more tolerable method.

ReconnectTM Directions:

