Demographic and recruitment information will be summarized. Frequency tables will be used to summarize toxicity and tolerability based on type, severity, and attribution of the adverse events during each condition. Clinical outcomes will be plotted and summarized for all subjects over time by individual and condition. Data summaries for missing and outlying data will be distributed and reviewed. Visual displays will be generated and presented to investigators in order to identify any outliers or other problems that could be missed by summary statistics. The categorical outcomes will be tabulated for each condition. The effect sizes of the changes of these clinical outcomes after 12 weeks will be estimated, using Cohen's definition, for each condition. Each phase will last for a total of 12 weeks. The effect size of active vs control condition will be calculated as the differences of the mean improvements between conditions, divided by pooled standard deviation of the improvements from the two groups.

Sample size and Randomization

This randomized crossover pilot study will have 28 subjects randomized into 2 orders of condition with a block size of 4 initially, then block size of 2 as the sample size nears

[figure not shown]
completion. Considering up to 15% early drop outs due to reasons not related to essential oils, we plan to randomize up to 33 subjects.

With 28 participants in this crossover study and using the participants as their own controls we estimate that we will be able to detect statistical significance with an effect size of **0.8.** In addition, we will compare the changes of the clinical outcome variables between Reconnect and control conditions by testing the interaction of condition and time based on a linear mixed model for repeated measurement, with conventional alpha of 0.05 for the primary outcome. In order to protect against Type 2 error in this pilot study, we will not correct for multiple tests.

Study Time Line

Study Timeline. The time-line for the study appears in Figure 1. The first several months will be used to obtain IRB approvals and create Case Report Forms or source documents. The next 19 months will be used for participant recruitment, supplementation, and assessment. Finally, the last 3 months will involve data analysis and manuscript writing.

Table 3. Study Timeline (24 months)

REFERENCES

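### Tolerability is summarised only from adverse events, so route switches, dilutions and stops without dropout that have no recorded adverse event are missing from the result

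*Combined protocol and SAP*

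**What the plan says.** **Aim.** Specific Aims/Hypotheses sets out to "examine preliminary data regarding benefit and tolerability of an essential oil formulation". Primary Hypothesis 3 then frames safety as a comparison of adverse events between the oil and the control. It names allergic contact dermatitis, contact urticaria and photosensitivity.

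**Early visits.** Study Design schedules visits every two weeks in the first month of condition 1, in part "to assess whether the mode of essential oils application is tolerable", by inhalation or on the skin. For condition 2 it treats that question as already settled.

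**Permitted changes.** Dosing gives every child both routes, but allows a change: "If a participant is unable to tolerate one of these delivery methods, then both the morning and night-time doses can be administered" by whichever method is better tolerated. Procedures adds: "The physician will discuss possible side effects and make dose or administration mode adjustments". The product directions foresee dilution for the most sensitive skin. Minimization of risk has a physician check for skin sensitivity and breast enlargement at each visit, "who may discontinue the oils or switch mode of administration based on clinical judgment".

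**Analysis.** The Data Analytic Plan says: "Frequency tables will be used to summarize toxicity and tolerability based on type, severity, and attribution of the adverse events during each condition". No other tolerability analysis is given. Table 1 has no row for route used, switch, stop or dilution.

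**The concern.** The most direct evidence that a child cannot tolerate a route is that the child is taken off it. The plan permits that step and devotes early visits to the question, but never counts the result. Intolerance reaches the planned summary only if someone records it as an adverse event.

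That cannot be assumed in these children. Procedures expects some to be too touch-sensitive to wear the actigraph, and the Short Sensory Profile is included to track sensory sensitivities. Refusing to have oil rubbed in, or objecting to a smell, is plausible and need not be written down as an adverse event.

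The pilot is meant to inform a larger multisite study. If route failures are not counted, the tolerability of the two-route regimen can be overstated when that study is planned.

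There is a secondary issue. The events named in Hypothesis 3 depend largely on skin exposure, and a switch changes that exposure. If switching differs between conditions, raw skin-event counts compare unequal amounts of topical use.

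**Working it through.** The plan gives no tolerability rate, switch rate or skin-event rate, so it has no figure on this point to reproduce. The check has two parts: what is captured, and an illustration of size.

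**1. What the plan captures**

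| Situation | Where it would appear |
|---|---|
| Skin reaction, then switch or stop | The reaction is in the adverse event table: elicited events are recorded whatever the suspected cause (Safety Measures), and a skin exam is scheduled from V3 to V10 (Table 1). The route failure itself is not shown. |
| Stop that becomes a dropout | Terminal evaluation, with the dropout pattern reported (Data Analytic Plan) |
| Switch for refusal of touch or smell, no adverse event recorded | No planned count |
| Dilution, no adverse event recorded | No planned count |
| Oil stopped, child stays in the study, no adverse event recorded | No planned count |

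The last three rows are the gap. The 85% adherence target does not close it, because adherence is not defined by route.

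**2. Size (switch counts assumed)**

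Inputs from the documents: 28 children experiencing both conditions; 12 weeks per condition. Assumed: k children cannot tolerate a route and switch at week 2.

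Route failure is k/28. The exact (Clopper-Pearson) 95% limits are the 2.5% point of Beta(k, 29 − k) and the 97.5% point of Beta(k + 1, 28 − k).

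| k | Route failure | Exact 95% CI |
|---|---|---|
| 2 | 7.1% | 0.9% to 23.5% |
| 4 | 14.3% | 4.0% to 32.7% |
| 6 | 21.4% | 8.3% to 41.0% |

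If none of these children had a recorded adverse event, the planned table could show 0 of 28 (upper 95% limit 12.3%).

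Topical child-weeks per condition without switching: 28 × 12 = 336. Each child who leaves topical use at week 2 removes 12 − 2 = 10.

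- k = 2: 336 − 20 = 316 (−6%)
- k = 4: 336 − 40 = 296 (−12%)
- k = 6: 336 − 60 = 276 (−18%)

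**3. Direction of the effect on skin events**

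Assume a 12-week skin-event risk r with constant hazard λ = −ln(1 − r)/12, and switches unrelated to a skin event. The expected number of children with a first event is (28 − k)r + k[1 − exp(−λt)]. Here t = 2 for a move to diffusion only. For a move to topical twice daily, t = 2 + 2 × 10 = 22, taking hazard as proportional to applications.

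| r | No switching | k = 4 to diffusion | k = 4 to topical |
|---|---|---|---|
| 10% | 28 × 0.1 = 2.80 | 2.40 + 4 × 0.0174 = 2.47 | 2.40 + 4 × 0.1757 = 3.10 |
| 20% | 28 × 0.2 = 5.60 | 4.80 + 4 × 0.0365 = 4.95 | 4.80 + 4 × 0.3357 = 6.14 |

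The count falls for one direction of switch and rises for the other.

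**The case against.** **Much intolerance is already captured.** The sentence under Minimization of risk concerns skin sensitivity and breast enlargement. A switch it prompts should normally follow an event already on a case report form, and a per-child count of that event is unaffected by the later switch. A stop that ends in dropout is evaluated for its relation to oils or procedures. Parents also rate satisfaction with each condition and its procedures. This stands. A reader might infer that an intolerable route leaves no trace at all, and the documents do not support that.

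**The effect on skin events has no fixed sign.** The Dosing rule works in both directions. A child who dislikes the smell may move to two topical doses, which raises skin exposure. Nothing limits switching to Reconnect, and refusal of rubbing could be as common on coconut oil. This also stands. A reader might infer that switching lowers the skin-event count or favours Reconnect. The documents do not say which switch is commoner, or in which condition.

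**Flexibility is part of the regimen.** Adverse events under a regimen that permits switching are a legitimate target, Hypothesis 3 is about adverse events, and this is a descriptive pilot. On the assumptions above with r = 10%, four switches move the expected count by about 0.3 of an event. This is fair for Hypothesis 3. It does not answer the separate tolerability aim, or explain why visits assess mode tolerability with no planned analysis of what they find.

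**Conclusion.** The point holds in a limited form. Non-adverse-event switches and dilutions, and stops in children who stay in the study, are missing from the planned tolerability result. The tolerability of the two-route regimen can therefore be overstated. Skin-event counts may also lose comparability between conditions if switching differs, in a direction that cannot be known from the documents.

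The size is illustrative only. With 4 of 28 assumed, a route failure of 14% (exact 95% CI 4% to 33%) could sit beside 0 of 28 in the adverse event table. That zero requires that none of the four had a recorded adverse event. If all four leave topical use at week 2, topical exposure falls by 12%.

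This is a cheap improvement worth making before data collection. It is not a flaw that invalidates the safety comparison.

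**What to change.** **Case report form.** At each visit in both conditions, record the route or routes used, and the date, direction and reason of any switch, stop or dilution. Condition 2 matters as much as condition 1: children randomised to the comparator first do not start Reconnect until week 16, and their next scheduled visit is week 20.

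**Data Analytic Plan, beside the adverse event tables.**
- By condition and route, tabulate the number and proportion (exact 95% CI) of children with a switch, stop or dilution because of intolerance. Count each as a failure of that route whether or not an adverse event was recorded.
- Show skin events beside topical child-weeks for each condition.

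The rule for when a child may switch or stop is not changed.

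**Cost.** One case report form field, one table, and a tolerability figure that may look less favourable.
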